3.4. Treatment Assignment & Blinding

At screening, after the participant has signed the informed consent form (ICF), the participant will be assigned a participant number sequentially based on the order in which the participant is screened into the study. This participant number will serve as the participant identification number on all study documents.

This is an open-label study. Blinding will only be employed for photograph review by an independent panel of physician reviewers with expertise in the areas of dermatology and/or plastic surgery.

3.5. Administration of Study Medication

[figure not shown]
Participants will undergo CoolSculpting treatment(s) in an outpatient clinical setting using CoolAdvantage and/or CoolAdvantage Petite applicators. Each participant will undergo a single treatment session that comprises timed segments of cooling followed by 2 minutes of manual massage. Each treated arm will have up to two timed segments (or cycles) in the treatment session, each treated thigh will have one timed segment (or cycle) in the treatment session. Treatments will be administered according to the Canadian CoolSculpting System User Manual.

[figure not shown]
3.6. Study Procedures and Flow chart

Participants will provide written informed consent before any study-related procedures are performed.

Participants who meet all of the inclusion criteria and none of the exclusion criteria shall be eligible to participate in the study and the first treatment will be scheduled.

All participants will be asked to maintain their weight by not making any major changes to their diet or exercise routine during the course of the study. If the weight change is more than 5% of total body weight at 12 weeks after the treatment, the participant's data will be excluded from the primary effectiveness analyses (but the participant will continue in the study).

This document is confidential.

4. Endpoints

4.1. Primary Endpoint

Correct identification of baseline versus 12-week treatment images of the upper arms by at least two out of three blinded, independent reviewers. Success will be defined as at least 75% correct identification of the pre-treatment images.

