9.1 Determination of Sample Size

In this study, both arms and thighs will be evaluated by independent raters. The independent raters' evaluations will be combined into one clinical judgement on each arm and thigh. The evaluations on arms and thighs will be considered as independent.

[Rivers 2018](#) described that the rate of correct identification was 83%. Using 75% as the lower bound of the 95% CI, the $\frac{1}{2}$ -width of the 95% CI will be 8%.

Based on these assumptions, we will need 60 evaluable arms or 32 evaluable participants for the arm evaluations with the assumption that less than 10% of participants have only one arm evaluation available. The same number of participants for thigh evaluations will be needed.

With an assumption that only 80% of all subjects will have both arms and thighs treated, we will need 38 evaluable participants in total for the study. Adding a 10% attrition rate, we will need to enroll 42 participants in the study.

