3.3. Determination of Sample Size

In this study, both arms and thighs will be evaluated by independent raters. The independent raters' evaluations will be combined into one clinical judgement on each arm and thigh. The evaluations on arms and thighs will be considered as independent.

A previous study described that the rate of correct identification was 83%. Using 75% as the lower bound of the two-sided exact 95% confidence interval (CI), the $\frac{1}{2}$ -width of the two-sided exact 95% CI will be 8%.

This document is confidential.

Based on these assumptions, we will need 60 evaluable arms or 32 evaluable participants for the arm evaluations with the assumption that less than 10% of participants have only one arm evaluation available. The same number of participants for thigh evaluations will be needed.

With an assumption that only 80% of all participants will have both arms and thighs treated, we will need 38 evaluable participants in total for the study. Adding a 10% attrition rate, we will need to enroll 42 participants in the study.

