8.1. Primary Effectiveness Analysis

The number and proportion of arms with correct identification of baseline vs. 12-week images of the upper arms by at least two out of three blinded, independent reviewers. Success will be defined as at least 75% correct identification of the pre-treatment images. The corresponding two-sided exact 95% CI of the proportion of arms with correct identification will be summarized.

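### The sizing states a lower 95% limit of 75%, but neither the success rule (an observed 75%) nor the 60 planned arms supplies it

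*SAP*

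**What the plan says.** **Sizing.** SAP 3.3 takes an expected rate of 83% from a previous study and continues: "Using 75% as the lower bound of the two-sided exact 95% confidence interval (CI"), with a half-width of 8 percentage points. From this it concludes that "we will need 60 evaluable arms or 32 evaluable participants for the arm evaluations", on the assumption that "less than 10% of participants have only one arm evaluation available". Protocol 9.1 makes the same calculation with less detail, "Using 75% as the lower bound of the 95% CI", and does not name the interval method.

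**Success rule.** SAP 4.1 says: "Success will be defined as at least 75% correct identification of the pre-treatment images". The same rule stands in the protocol synopsis, Protocol 5.2 and SAP 8.1, and SAP 10 applies it again in the analysis by generation. None of these places ties it to a confidence limit.

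**Role of the interval.** SAP 8.1 says: "The corresponding two-sided exact 95% CI of the proportion of arms with correct identification will be summarized". It is a reported quantity and not part of the rule.

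**Status of the analysis.** SAP 2 describes all analyses as descriptive, with no hypothesis testing. SAP 12 makes the arm the unit of analysis. Its list of changes from the protocol does not mention the two uses of 75%.

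**The concern.** One figure has two roles for the same endpoint. In the sizing, 75% is where the lower end of the interval should fall if the observed rate is 83%. In the success rule, 75% is the value that the observed rate itself must reach. A result can meet the second and be far from the first.

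The sizing statement is also not true of the planned number. A reader who takes SAP 3.3 at its word expects an observed 83% in 60 arms to come with a lower limit of 75%. It does not.

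This matters because the 75% rule is the only success criterion in the plan, and Protocol 4.2 says the data will help support a regulatory submission. If success is reported beside the sizing paragraph as written, the result may be credited with more than it shows.

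**Working it through.** **Inputs.** Expected rate p = 0.83, half-width d = 0.08, target lower limit 0.75 and 60 arms (SAP 3.3). Success if the observed proportion is at least 0.75 (SAP 4.1). Two-sided exact (Clopper-Pearson) 95% interval (SAP 3.3 and 8.1). Arms are treated as independent unless stated otherwise.

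**Step 1: reproduce the 60.** The usual precision formula is n = z² p(1 − p) / d².

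- With z = 1.645 (a one-sided 95% limit, the same as a two-sided 90% interval): 2.706 × 0.1411 / 0.0064 = 59.7, so 60. This matches the plan.
- With z = 1.96 (two-sided 95%): 3.842 × 0.1411 / 0.0064 = 84.7, so 85.
- With the two-sided exact limit that the SAP names, an observed 83% needs about 119 arms for a lower limit of 75%.

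The later step to participants agrees: 60 / 1.9 = 31.6, so 32. The stated 60 therefore matches a one-sided normal approximation and not the interval that the SAP describes.

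**Step 2: what 60 arms give.** The exact lower limit for x out of n is the 0.025 quantile of Beta(x, n − x + 1). The upper limit is the 0.975 quantile of Beta(x + 1, n − x).

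| Result | Observed | Exact 95% CI | Success as written? | Lower limit at least 75%? |
|---|---|---|---|---|
| 45/60 | 75.0% | 62.1% to 85.3% | yes | no |
| 50/60 | 83.3% | 71.5% to 91.7% | yes | no |
| 51/60 | 85.0% | 73.4% to 92.9% | yes | no |
| 52/60 | 86.7% | 75.4% to 94.1% | yes | yes |

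The planned result, about 50/60, misses the stated lower limit by 75 − 71.5 = 3.5 points. The smallest success misses it by 75 − 62.1 = 12.9 points. Results from 45 to 51 are declared successes whose lower limit is under 75%.

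**Step 3: how often success is declared.** P(X ≥ 45) for X ~ Binomial(60, true rate):

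| True rate | P(45 or more) | P(52 or more) |
|---|---|---|
| 65% | 6.6% | less than 0.1% |
| 70% | 24.4% | 0.2% |
| 75% | 56.9% | 2.1% |
| 83% | 96.0% | 28.8% |

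At the planning rate of 83%, the chance of a result from 45 to 51 is 96.0% − 28.8% = 67.2%. This is the expected region and not an edge case.

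**Step 4: both arms of one person.** The documents give no within-participant correlation, so a range is assumed. With 30 participants and two arms each, the effective number of arms is 60 / (1 + ρ): 60 at ρ = 0, 40 at ρ = 0.5 and 30 at ρ = 1. Simulated P(success) at a true 70% lies between about 24% and 30% over that range. At ρ = 0.5 it is about 11% at a true 65% and 92% at a true 83%. Positive correlation makes the honest interval wider than in step 2.

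**The case against.** The strongest reply is that nothing here contradicts anything else. The sizing is a precision calculation. It does not mention success, power or a claim. SAP 2 rules out hypothesis testing. A planning half-width and an acceptance threshold may share a number, and the success rule is worded the same way wherever it appears, so the analyst has no doubt about what to do. The exact interval is reported directly after the verdict, so a 45/60 result would appear with its 62.1% lower limit in view.

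Most of this stands. A reader might infer that the plan promises 95% confidence in a true rate of at least 75% and then fails to test for it. The documents do not support that, because no section says that success demonstrates such a rate. A reader might also infer that the rule ignores the interval altogether. That is true of the rule but not of the reporting. Nor should the 28.8% in step 3 be read as a power shortfall of the planned analysis: no lower-limit rule is planned and no power is stated. Part of that low figure comes from the sizing, since at 119 arms the same lower-limit rule (99/119 or more) would be met about 54% of the time at 83%.

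What the reply does not meet is the precision statement. The SAP says that the two-sided exact lower limit will be 75% at the assumed 83%, and with 60 arms it is 71.5%. Nor does any text say how a verdict at 75% relates to a sizing target at 75% for the same endpoint.

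**Conclusion.** The point holds as a mismatch between a stated property and the design. The sizing states a lower 95% limit of 75%. The success rule does not require it, and 60 arms do not supply it at the planning rate (71.5% at 50/60). A success at the threshold is compatible with true rates from 62.1% to 85.3%, and a true rate of 70% would be called a success about one time in four.

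A reader might go further and conclude that the success rule is invalid or that the trial must be enlarged. The documents do not support this: a descriptive threshold on an observed proportion is permissible in a study that disclaims testing, provided it is described as one.

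The intervals and binomial probabilities rest on 60 evaluable arms treated as independent. Positive correlation within participants would widen the intervals and would, if anything, raise the chance of success at 70%. The one-sided origin of the 60 is an arithmetic match and is not stated in the documents.

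**What to change.** 1. **Protocol 9.1 and SAP 3.3.** Replace the statement of a 75% lower limit and 8-point half-width with the precision that 60 arms give: an exact 95% interval of about 71.5% to 91.7% at 50/60, treating arms as independent, and wider if a participant's two arms are correlated. State that success is a descriptive threshold on the observed proportion, with probability of about 24%, 57% and 96% at true rates of 70%, 75% and 83%.
2. **SAP 8.1 and SAP 10.** State that meeting the threshold does not show a true rate of at least 75% unless the exact lower limit already being reported is at least 75%. In the overall analysis of 60 arms this means 52/60 or more. In the analysis by generation the count depends on the subgroup size.

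The cost is wording in both documents, so a protocol edit as well as a SAP edit, and no extra participants. The sponsor also accepts a less favourable claim for results of 45 to 51 out of 60. The success rule and the sample size can stay as they are.

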4.2. Secondary Endpoints

1. Correct identification of baseline versus 12-week treatment images of the inner thighs by at least two out of three blinded, independent reviewers.
2. Participant response of 'satisfied' or 'very satisfied' for question 1 (overall satisfaction) on the following CoolSculpting participant questionnaires at the 12-week visit:
 - a. Upper arms
 - b. Inner thighs
3. Fat reduction using caliper measurements at 12-weeks compared to baseline for the following areas:
 - a. Upper arms
 - b. Inner thighs

4.3. Safety Endpoints

1. Adverse Events (AEs), including Serious Adverse Events (SAEs); and Adverse Device Events (ADEs), including Serious Adverse Device Events (SADEs).

This document is confidential.

5. Populations for Analyses

5.1. Enrolled Population

All screened participants who provide informed consent, receive participant ID, and provide demographic and/or baseline screening information, regardless of the participant's randomization and treatment status in the study.

5.2. Safety (SAF) Population

The safety population will consist of all the treated participants.

5.3. Per Protocol (PP) Population

The PP population will consist of all treated participants followed for 12 weeks and with weight change of no more than 5% of total body weight at the time the 12-week images are taken.

This document is confidential.

6. General Aspects for Statistical Analysis

6.1. General Methods

- [REDACTED] will be used to produce all listings, summaries, and analyses described in this document.
- Unless otherwise specified, summaries will be presented for each treatment area and overall.
- Continuous variables will be summarized using the number of participants with observed values (n), mean, standard deviation (SD), median, 1st and 3rd quartiles (Q1, Q3), minimum (min), and maximum (max). Categorical variables will be summarized using number of observations (n), frequency and percentages of participants.
- All relevant participant data will be included in listings. All participants entered into the database will be included in participant data listings.
- Unscheduled assessments for visit based parameters will be listed but not summarized or analyzed; only data recorded on the nominal study visits will be included in summaries and analyses.
- Medical history data will be listed for the Enrolled Population sorting by participant number, start date (placing missing and partial dates first) and end date, then alphabetically by System Organ Class (SOC) and Preferred Term (PT) within SOC.
- Prior and concomitant medications will be listed for the Enrolled Population, sorted by participant number, start date (placing missing and partial dates first) and end date, alphabetically by Anatomic Therapeutic Chemical (ATC) level 2 category and then by preferred name within ATC level 2 category.
- All AEs will be listed, sorting by participant number, start date (placing missing and partial dates first) and end date, alphabetically by SOC, and then by PT within SOC. AE duration in days will be calculated as (end date - start date + 1) and included in the data listings.

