Third Degree Burn	Third degree burns are deeper still, involving all layers of the skin. Because the nerves and blood vessels are damaged, third degree burns appear white, leathery, and tend to be relatively painless.
Cold-induced Panniculitis	Severe inflammation which requires medical or surgical intervention.
Skin Pigment Changes	The appearance of hyperpigmentation or hypopigmentation in the treatment area.
Infection	Infection at the treatment site, diagnosed by a physician and requiring medical intervention.
Discomfort During Procedure	Discomfort reported during the procedure that is intolerable to the participant and results in an interruption or discontinuation of the procedure
Discomfort Post Procedure	Significant discomfort, pain, cramping, tenderness, soreness, muscle spasm following the procedure which results in medical intervention (physician visit and/or prescription pain reliever)
Prolonged Sensory Alteration Post Procedure	Sensory changes (numbness, tingling, burning sensation) that are prolonged (ie, lasting longer than 12 weeks).
Sensory Alteration Requiring Medical Intervention	Sensory changes (pain, burning, stinging, hypersensitivity) with a severity warranting medical intervention.
Vasovagal Symptoms	The occurrence of symptoms of anxiety, light-headedness, dizziness, nausea, sweating, near syncope, or syncope (fainting).
Contour Irregularity	Significant indentation or contour irregularity in the treatment area that would require surgical intervention.
Allergic/Irritant Contact Dermatitis	Itchy rashes and skin peeling that may result from prolonged exposure to gel pad or applicator pressure
Subcutaneous Induration	Hardness within the treatment area, either as general firmness or discrete nodules.
Paradoxical Hyperplasia	Visibly enlarged tissue volume within the treatment area which may develop 2-5 months after treatment.
Hernia	Creation or exacerbation of hernia. Hernia is defined as a protrusion of an organ or the fascia of an organ through the wall of the cavity that normally contains it.
Treatment Area Demarcation	Treatment area demarcation: excessive fat removal in the treatment area causing unwanted indentation
Other	Any other untoward medical event determined by the investigator to be an adverse event, regardless of the relationship to the device or treatment.

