8.2 Safety Assessments

Throughout the course of the study, all AEs will be monitored and reported on an AE CRF, including seriousness, severity, action taken, and relationship to study treatment. If AEs occur, the first concern will be the safety of the study participants.

Safety will be monitored by documentation of AEs and clinical assessment of the treatment sites. Post-treatment sensory changes outside of treatment areas will also be documented and assessed.

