8.2.1 Adverse Events

Throughout the course of the study, all AEs will be reported and monitored on an AE CRF, including event name, duration, seriousness, relatedness, severity, action taken, and outcome. If AEs occur, the first concern will be the safety of the study participants. AEs and device deficiencies are to be recorded on the corresponding CRF for the participant upon the site becoming aware of said event. Additionally, SAEs and UADEs will be reported using SAE forms within 24 hr of awareness.

AEs will be collected throughout the study once there is a signed ICF. At each visit, the investigator or designated study staff will solicit and assess the participant for AEs. Previously recorded AEs and changes in therapy/concomitant medications are to be updated as necessary. All reportable AEs and clinically significant abnormal laboratory findings will be documented on the appropriate CRF.

Adverse Event Definition

An AE is defined in accordance with ISO 14155 as any untoward medical occurrence, unintended disease or injury, or untoward clinical signs (including abnormal laboratory findings) in participants, users, or other persons, if related to the investigational medical device. This definition includes events related to the investigational medical device or comparator and events related to the procedures involved. Disease signs and symptoms that existed before the study treatment are not considered AEs unless the condition recurs after the participant has recovered from the pre-existing condition or the condition worsens in intensity or frequency during the study.

AEs will be monitored throughout the study once the participant has signed the ICF. At each post-baseline visit, the investigator will begin querying for AEs by asking each participant a general, non-directed question such as “Have you had any changes to your condition since your last visit?” Previous AEs and changes in therapy/concomitant medications are to be updated. Directed questioning and examination will then be done as appropriate. All reportable AEs and clinically significant abnormal laboratory findings will be documented on the appropriate eCRF.

Adverse Device Event

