6.4. Visit Windows

Data collected at unscheduled visits that occurred outside the time windows specified in the protocol (e.g., post-dose laboratory tests done on days not specified in the protocol) will be included in the data listings but will not be included in the analyses.

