8.2. Secondary Effectiveness Analysis

[figure not shown]
The number and proportion of thighs with correct identification of baseline vs. 12-week images of the inner thighs by at least two out of three blinded, independent reviewers and the corresponding two-sided exact 95% CI of the proportion of thighs with correct identification will be summarized.

Participants who have reported 'Very satisfied' or 'Satisfied' on each of the CoolSculpting participant questionnaires (upper arms and inner thighs) for question #1 (overall satisfaction) will be categorized as 'Satisfied.' The numbers and proportions of 'Satisfied' at 12-weeks visit will be summarized and two-sided exact 95% CI of the proportions will be provided for arms and thighs, respectively.

Fat reduction using caliper measurements at 12-weeks compared to baseline for upper arms and inner thighs will be summarized descriptively using the change from baseline to week 12 for arms and thighs,

This document is confidential.

respectively. Also, two-sided 95% CI of the mean change from baseline vs. Week 12 will be provided for arms and thighs, respectively.

This document is confidential.

9. Safety

The population used for safety analyses will be the Safety Population (SAF).

Safety will be assessed on the basis of adverse event (AE) or adverse device event (ADE), and other safety assessments.

The numbers and proportions of participants with TEAEs, Serious TEAEs, ADEs, SADEs, unanticipated ADEs, and unanticipated SADEs will be summarized. The numbers and proportions of participant-reported pain scores (0 to 10 scale) will be summarized.

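### SAP 6.1 keeps pain scores and treatment-site assessments from unscheduled visits out of every summary, with no visible safety exception; a worst-value row would close this minor gap

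*SAP*

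**What the plan says.** SAP 6.1 (General Methods) sets the rule for what is tabulated: "Unscheduled assessments for visit based parameters will be listed but not summarized or analyzed; only data recorded on the nominal study visits will be included". It applies to visit-based parameters of every kind, and the visible text makes no separate provision for safety.

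SAP 6.4 (Visit Windows) has a second rule, listing but not analysing "Data collected at unscheduled visits that occurred outside the time windows specified in the protocol". Its only example is laboratory tests.

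Two safety measures look visit-based. SAP 9 plans that "The numbers and proportions of participant-reported pain scores (0 to 10 scale) will be summarized", and Protocol 8.2 states that "Safety will be monitored by documentation of AEs and clinical assessment of the treatment sites".

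Adverse events follow a different path. Protocol 8.2.1 says "AEs will be collected throughout the study once there is a signed ICF", and sites record them when they become aware of them. SAP 9.2 classes an event as treatment-emergent by its start date.

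**The concern.** An unscheduled visit is unlikely to be a random occasion. A participant who comes back between planned visits may well do so because the treated area hurts or looks wrong. A rule that tabulates only planned visits can then omit a value because of what the value is, and the omission runs in the device's favour.

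The adverse event tables close only part of this gap. Protocol 4.2.1.2 does not treat mild-to-moderate bruising, swelling, discomfort, tenderness or soreness at the site as adverse events when they settle shortly after the procedure. For these effects the pain score and the site assessment are the visible measures, and a captured adverse event carries only a mild, moderate or severe grade, not the 0-10 score. Safety is half of the study objective, and the data are meant to support a regulatory submission from a single open-label cohort.

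**Working it through.** There is no figure in the plan to reproduce. The check is to follow each safety data stream through the summary rules.

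1. **Adverse events and adverse device events.** These are the safety endpoints named in Protocol 5.2 and SAP 4.3. They are collected throughout the study (Protocol 8.2.1) and tabulated by start date, with a default to treatment-emergent when the date is unclear (SAP 9.2). SAP 6.1 is limited to visit-based parameters. Result: no event is lost from the tables.

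2. **Pain score, 0-10.** It is summarized under SAP 9. If it is a visit-based parameter, a score taken at an unscheduled visit is listed and not summarized under SAP 6.1.

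3. **Treatment-site assessment.** Protocol 8.2 names it as part of safety monitoring. The same rule gives the same result. A finding severe enough to be an adverse event is still counted under step 1.

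4. **What falls between.** An anticipated effect that stays mild to moderate, is not judged to disrupt daily activities and is gone by the next planned visit is not an adverse event (Protocol 4.2.1.2) and is in no by-visit table (SAP 6.1). It remains in listings only.

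5. **SAP 6.1 against SAP 6.4.** Section 6.1 excludes every unscheduled assessment of a visit-based parameter. Section 6.4 names only unscheduled visits outside the protocol windows, so it is narrower on that axis. It speaks of data in general, so it is broader in subject. An unscheduled assessment inside a window is excluded by 6.1 and not mentioned by 6.4.

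**Scale, by assumption.** Let k be the number of participants whose worst score is seen only at an unscheduled visit. Take N = 42, the planned enrolment, as if all were treated. The proportion with that score is understated by k/N:

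| k (assumed) | k/42 | Understatement, percentage points |
|---|---|---|
| 0 | 0/42 | 0 |
| 1 | 1/42 | 2.4 |
| 2 | 2/42 | 4.8 |
| 4 | 4/42 | 9.5 |

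The documents do not show which row applies.

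**The case against.** The strongest reply is that the problems most likely to bring someone back are already routed to adverse events. Blistering falls under second-degree burn in Protocol 4.2.1.2. Significant discomfort after the procedure is a listed potential adverse effect, in an entry that ends "muscle spasm following the procedure which results in medical intervention (physician visit and/or prescription pain reliever". Anticipated effects that disrupt daily activities are evaluated as potential adverse effects. Tabulating planned visits only also keeps by-visit denominators comparable, every analysis is descriptive (SAP 2), and with about 42 participants the unscheduled values can be read in the listings.

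Most of this stands. A reader might infer that the overall safety summary is biased. The documents do not support that, because the tables for the named safety endpoints do not depend on visit type. Nor does SAP 6.4 remove planned visits held outside their window; it speaks only of unscheduled ones.

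A reader might also take the wide spread of pain results in the cited studies as evidence that the omission is material. In the two arm studies the mean scores near 1 were recorded during treatment or before discharge. The mean of 7 in the Thai arm and thigh study is reported together with pain during and after the procedure. Scores taken on the treatment day belong to a planned visit, so the rule would not touch them. The follow-up scores in the 15-subject arm study were all 0 at weeks 1, 4 and 12, which gives no evidence of later pain prompting a return.

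What the reply does not remove is the mild-to-moderate band. Moving an effect from anticipated to adverse event rests on judgement, and the boundary is not sharp: Protocol 8.2.1 defines a moderate event as one that interferes with everyday activities, while 4.2.1.2 exempts moderate skin effects unless they disrupt them. The protocol also does not say whether an unscheduled study visit counts as the physician visit in the discomfort entry.

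**Conclusion.** The point holds as a minor one. As written, SAP 6.1 would leave any pain score or treatment-site assessment from an unscheduled visit out of the summaries, and anticipated effects that are not adverse events and are seen only there would be summarized nowhere. If symptoms prompt such visits, the pain and site summaries lean toward the device. The adverse event and adverse device event tables are sound on this point.

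This rests on three assumptions: that pain and site assessments are treated as visit-based parameters, that they are in fact taken at unscheduled visits, and that the redacted SAP 9.6 does not already cover the case. The assessment schedule is not visible either, so none of these can be confirmed, and the redaction is not a fault of the plan. The size may be zero; each affected participant would be worth about 2.4 percentage points.

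**What to change.** Before database lock:

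- **SAP 6.1:** keep the rule for effectiveness parameters and for by-visit tables, so that their denominators do not change.
- **SAP 9:** unless SAP 9.6 already does so, add one row for each visit-based safety measure (pain score, treatment-site assessment) giving the worst post-treatment value per participant over all scheduled and unscheduled assessments. Define when the post-treatment period starts, so that it is clear whether scores on the treatment day count toward the worst value.
- **SAP 6.4:** align it with 6.1 on unscheduled assessments that fall inside a window, and state that neither section removes adverse events or adverse device events from the tables.

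The cost is a few sentences and one extra row per measure. SAP 6.1 already sends unscheduled assessments to the listings, so any that are collected need no new data capture. The price to the sponsor is that worst-value figures may look slightly less favourable than the by-visit figures. If no unscheduled assessments occur, the new row simply gives the worst scheduled value.
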